Usual Care (UC) will include the multidisciplinary health care, education and supports that are routinely available to Nemours families of youth with T1D. This includes ~quarterly clinic visits with a pediatric endocrinologist or advanced practice nurse, with referrals to a certified diabetes educator, dietitian, social worker or psychologist as deemed clinically necessary by that HCP. T1D visit data will be extracted from Nemours EMR for each adolescent. Parental reports of care received elsewhere will be recorded. An EMR "Smart Form" used in several of [name] studies enables electronic capture of granular T1D visit data. Over 90% of Nemours T1D patients are on intensified regimens, i.e., insulin pump (~60%) or multiple daily insulin injections (~40%) using a "basal-bolus" approach and dietary carbohydrate counting. Treatment targets are HbA_{1c} $<$ 7.5% ($<$ 7.0% if deemed safe by attending MD) and minimization of symptomatic or severe hypoglycemia. A small, but growing, number of patients use continuous glucose monitors as part of their care.

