Transdisciplinary Care: In Person (TC-IP) versus Telehealth (TC-TH) Delivery TC-IP involves face-to-face sessions with the TC team meeting together with the family at the diabetes clinic. TC-TH will be the same as TC-IP except T1D visits will occur with families at their homes or other remote location via a HIPAA-compliant telehealth platform such as American Well AW9 (<https://www.americanwell.com/aw9-launched-at-himss/>). This platform has been used by Nemours CareConnect in Florida since 2015 and in Delaware since May, 2016. Patients/parents can access CareConnect from any PC, Apple or Android device. Technical support from Nemours Telehealth is budgeted.

FIGURE 2. STUDY DIAGRAM OF REVISED RANDOMIZED CONTROLLED TRIAL

Changes to Experimental Design and Treatment Conditions related to COVID-19 Precautions In March of 2020, Nemours began transitioning all T1D clinical care visits to telehealth as a precaution against spread of the novel coronavirus, COVID-19. About one third of the families randomly assigned to TC-IP had completed the study. Those randomized to TC-IP and part way through the study and those recently randomized to TC-IP were not able to complete face-to-face visits. After considering the options of: 1) halting delivery of all TC care across all arms of the study until in person care was possible again; and, 2) providing TC-IP families with TC delivered through telehealth, our study DSMB recommended the latter. Because we could not predict when in person visits would again be allowed and suspending TC care would result in a smaller “dose” of the experimental treatment, the option to alter delivery mode was chosen to gather as much information as possible about the potential efficacy of TC and to explore additional questions about mode of delivery (e.g., feasibility, family preference).

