Families who had already received some TC-IP visits were transitioned to receiving TC through telehealth and were reclassified as “TC-IP/TH.” Those randomized to TC-IP who had received no TC-IP visits but were due for clinical care also received TC through telehealth and moving forward will be allowed to choose (to the extent allowed by precautions) whether they want to receive TC visits in person or remain with telehealth. They are being tracked as “TC-TH/CH.” See Figure 2 above. Because these new arms of the study will be small and combine IP and TH delivery of TC, all TC arms of the study will be combined for primary comparisons against UC and comparisons will be made between the TC groups (size permitting) to explore whether delivery mode is important for outcomes. It is important to note that UC appointments are, for now, also being delivered through telehealth. This previously available option for UC was not widely used.

TC Team Training: An optimal test of TC requires that team members have requisite knowledge, skills and practical experience at trial initiation. Careful training also promotes integrity of the TC arms of the study. Key elements of TC are sharing of knowledge and skills among disciplines and lowering of inter-professional boundaries. TC team training will comprise: 1.) Knowledge of TC and its distinction from other models; 2.) Teaching one another about the evidence base and clinical practices for each of the team’s professions; and 3.) Experiential learning in applying TC with simulated patients and then actual clinical cases. Reaching agreement on what comprises TC is also a prerequisite to achieving it in the RCT. TC team members will discuss directed readings,^{282,283} categorize hypothetical programs as Multi-, Inter- or Trans-Disciplinary models, and interview colleagues about T1D care at their institutions and evaluate them from a TC perspective. Qualitative interviews of team members during the RCT will guide refinements to TC training and implementation, yielding an empirically validated TC curriculum for future RCTs.

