Hypothesis 6: TC-TH adolescents will keep significantly more appointments than either TC-IP or UC youths.

Limitations: Aspects of this application could have been done differently: 1.) Randomization at the level of patients/families was selected over randomizing sites in a Cluster RCT design. A Cluster RCT could reduce the potential for contamination, but it introduces problems in that differences between Nemours sites could obscure detection of treatment effects. We opted for randomization of patients/families to treatments with concomitant efforts to minimize possible contamination. Since this funding mechanism seeks to develop preliminary data to support a larger multi-site RCT in the future, empirical evaluation of our success in detecting, preventing and managing possible contamination effects would be an important feature of a future application of that type. 2.) The original structure of the RCT as a 3-arm trial (UC vs TC-IP vs TC-TH) introduces added complexity and expense and may decrease the sample size available for each study arm. Since telehealth delivery of subspecialty care for chronic conditions may be the wave of the future, it is prudent to capitalize on the availability of the DP3 mechanism to provide initial data on if and how telehealth delivery of the proposed TC intervention may be superior to conventional face to face delivery of that same care. Unfortunately, precautions due to COVID-19 spread has limited the TC-IP arm of the trial but comparisons are possible between UC and TC-TH as originally planned. 3.) The enrolled sample represents a period of marked developmental change. We have not planned specific adaptations to the TC model, but a key role of the Psychology Post-Doctoral Fellow will be assurance that negotiated interventions are developmentally appropriate for each adolescent.

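### Usual Care also moved to telehealth in March 2020, so TC-TH vs UC no longer has the planned comparator and Hypothesis 6 averages over two of them

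*Combined protocol and SAP*

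**What the plan says.** All references are to section 3.4 of the combined protocol and SAP.

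- **Usual Care paragraph.** UC is the multidisciplinary care routinely offered to Nemours families. "This includes ~quarterly clinic visits with a pediatric endocrinologist or advanced practice nurse"; telehealth is not mentioned there.
- **TC-IP versus TC-TH paragraph.** "TC-TH will be the same as TC-IP except T1D visits will occur with families at their homes or other remote location".
- **COVID-19 changes.** "In March of 2020, Nemours began transitioning all T1D clinical care visits to telehealth". On the comparator: "It is important to note that UC appointments are, for now, also being delivered through telehealth", followed by "This previously available option for UC was not widely used".
- **Limitations, item 2.** After noting that COVID-19 restricted the in-person arm, the text says that "comparisons are possible between UC and TC-TH as originally planned".
- **Hypothesis 6.** "TC-TH adolescents will keep significantly more appointments than either TC-IP or UC youths".
- **Analytic Plans.** Mixed models are planned for the listed hypotheses. Treatment group and demographics are fixed effects; site, physician and within-subject effects are random. The TC arm is divided into four secondary groups by delivery mode, to be analysed if numbers allow. UC remains one group.

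**The concern.** The Limitations sentence mentions COVID-19, so it was written for this revision and is not leftover text. It treats the disruption as a problem of the TC-IP arm only, although the COVID-19 subsection reports that UC changed delivery mode as well. The plan follows the change of mode on the TC side, by reclassifying and pooling arms. It has no counterpart on the UC side: no period term, no visit-mode term and no analysis before and after March 2020.

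Hypothesis 6 is the most exposed. Remote delivery is one plausible reason for TC-TH families to keep more appointments, and that reason disappears at visits where UC is also remote. A null overall result could then be taken to mean that telehealth does not help attendance, when part of the contrast had been removed by the change in UC.

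**Working it through.** The plan gives no figure for this point, so the check is first a comparison of passages and then an illustration of size.

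**Step 1. What differs between TC-TH and UC in each period**

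| Period | TC-TH | UC | Arms differ in |
|---|---|---|---|
| Before March 2020 | TC model, remote | Usual model, mainly in clinic | Care model and mode |
| After the switch | TC model, remote | Usual model, telehealth | Mainly care model |

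The first row is the planned contrast and the second is not. Recruitment closed at the end of March 2020 (Sample Size and Statistical Power) and each family is followed for about 12 months (Experimental Design). Late recruits therefore have nearly all their follow-up in the second row, and some families cross from one row to the other.

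**Step 2. How the overall contrast behaves**

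Let *a* be the care-model contribution to the difference in appointments kept, *m* the contribution of remote delivery, and *f* the share of UC appointments held by telehealth. Assume that *a* and *m* add.

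- In-clinic UC: difference = *a* + *m*
- Telehealth UC: difference = *a*
- Overall: (1 − *f*)(*a* + *m*) + *f a* = *a* + *m*(1 − *f*)

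Only the mode part is diluted. As an illustration with assumed values that are not in the documents, take 80% kept in person, 90% kept by telehealth and *a* = 0. The expected difference is 10 × (1 − *f*) points:

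| *f* | 0 | 0.25 | 0.50 | 0.75 | 1 |
|---|---|---|---|---|---|
| Difference (points) | 10 | 7.5 | 5 | 2.5 | 0 |

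**Step 3. A rough value for *f***

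The documents give no *f* for UC. The only anchor is that about one third of TC-IP families had finished when the change came. Assume that UC accrued uniformly and in parallel with TC-IP over *T* months ending at the switch, and that the switch was immediate, complete and lasting.

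- Fraction complete = 1 − 12/*T*. Setting this to 1/3 gives *T* = 18.
- Share of month-*v* visits after the switch = *v*/*T*: 3/18 = 0.17, 6/18 = 0.33, 9/18 = 0.50, 12/18 = 0.67.
- Mean over the four follow-up visits = (0.167 + 0.333 + 0.500 + 0.667)/4 = 0.42.

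With *f* = 0.42 the 10-point illustration becomes 10 × 0.58 = 5.8 points. Taking *T* = 12 or *T* = 24 gives means of 0.62 and 0.31, but these imply 0% and 50% complete at the switch, so neither fits the one-third anchor. A gradual switch, or a return of UC to clinic, would lower *f*; UC telehealth before March 2020 would raise it.

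**Step 4. Whether the plan handles it**

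No term in the Analytic Plans model distinguishes the two rows of Step 1. Pooling the TC arms does not either, and the pooled TC vs UC comparison uses the same mixed UC arm.

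**The case against.** The strongest reply has four parts.

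- **The change is disclosed and randomisation is untouched.** Families randomised concurrently to UC and TC-TH lived through the same calendar period. This stands. A reader might infer that the comparison is invalid or impossible; the documents do not support that. What changed is the quantity being estimated.
- **UC means whatever care is routinely available, and telehealth was already an option.** This is a defensible treatment-policy reading, and the Limitations phrase may mean only that these two arms kept their assignment. But the plan never states that reading, and Hypothesis 6 is not interpreted in its light.
- **TC-TH vs UC always combined care model with mode.** This is correct. A reader might infer that the switch created this confounding, or that visits before the switch would give a clean telehealth-versus-clinic answer. Neither holds: the confounding was in the three-arm design from the start, and the mode contrast is TC-TH vs TC-IP, the other half of Hypothesis 6.
- **Splitting one-year outcomes by visit date is unsound.** This also stands. A 12-month HbA1c or questionnaire score may reflect care from both periods, and period is entangled with time on study and with the pandemic. With 35 UC patients in the power calculation, such a split would also be imprecise. The argument has much less force for appointment keeping, where each appointment has its own due date.

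**Conclusion.** The point holds in a limited form. The claim that UC vs TC-TH survives as planned conflicts with the document's own account of what happened to UC. Hypothesis 6 and its model do not carry the change through. The comparison remains randomised and usable as TC-TH vs UC as delivered. Its planned form, against in-clinic UC, is available only for visits due before the switch.

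The loss is *m* × *f*: the mode-related part of the attendance advantage times the share of UC visits held by telehealth. Neither quantity is in the documents. The value of about 42% rests on uniform accrual, parallel arms, one third complete in UC as in TC-IP, and an immediate, lasting switch. It shows that the share need not be small and should not be cited as the trial's figure. The inconsistency itself needs none of these assumptions.

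The matter deserves correction but does not threaten the primary analysis. Appointment keeping is not among the primary or secondary endpoints named in Analytic Plans, and secondary-group contrasts are conditional on sample size.

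**What to change.** 1. **Limitations, item 2.** Replace the phrase with wording such as: *UC was delivered mainly in clinic before March 2020 and by telehealth afterwards; the originally planned contrast of TC-TH with in-clinic UC is available only for visits due before the switch.*
2. **Hypothesis 6.** Keep the overall randomised comparison, defined as TC-TH vs UC as delivered. Add a pre-specified arm-by-period estimate for appointments due before and after the switch. Use visit dates and, where recorded, delivery mode from the EMR in every arm. State that a null overall result is not evidence that telehealth has no effect on attendance.
3. **Interpretation.** Draw no pure telehealth-versus-clinic conclusion from UC vs TC-TH in either period. Leave that question to TC-TH vs TC-IP before the switch.
4. **HbA1c and questionnaire outcomes.** Report the delivery mode of UC visits and add at most a supportive pre/post sensitivity analysis.

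The cost is modest. Table 3 already schedules appointment keeping at every quarterly visit, and T1D visit data are already extracted from the EMR. The document does not say that delivery mode is recorded for UC visits, so this needs confirming; visit dates are the fallback. The statistical price is precision, because period-specific estimates rest on fewer visits.

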6. PROTECTION OF HUMAN PARTICIPANTS

Nemours' Office of Human Subjects Protection is nationally accredited by the Accreditation Agency for Human Research Protection Programs (AAHRPP) and is one of the few strictly pediatric programs to have attained this distinction. NOHSP operates two Institutional Review Boards under its Federal-Wide Assurance: Nemours IRB 1, and Nemours IRB 2, which was chaired by [name] (FWA# 00000293). Since the two IRBs are each empowered to review and approve research occurring at any Nemours location, the present research will be submitted to the Nemours IRB 1 as the IRB of record and [name] will recuse himself from deliberations related to this work.

The proposed research consists of both qualitative (crowdsourcing and qualitative interviews) and quantitative (RCT) components. These two components of the application are treated separately in the section below.

Human participants' involvement, characteristics and design

Qualitative research component: About 100-120 adolescents with T1D, and 100-120 of their parents, and ~30 T1D HCPs will be recruited via flyers mailed to U.S. T1D referral centers, e-mails to T1D HCPs, internet announcements, and handouts at national conferences to constitute the membership of the respective crowds. Current Nemours T1D patients who are at least 16 years old and who otherwise meet the eligibility criteria for the RCT portion of the proposed work, (and their parents) will also be recruited for this component, since the patients would be too old to be eligible for the planned RCT. The intent is to enlist as many members as possible who are not affiliated with Nemours as a patient, parent or HCP so that prospective Nemours participants remain naïve to the RCT aims and procedures and thus remain eligible for participation in the RCT. Parents, adolescents and HCPs will enroll as members of the pertinent Crowd after authenticating an IRB-approved electronic parental permission, adolescent assent or informed consent form, as was done for our current NIH DP3 grant and PCORI-funded shared decision making study. About 5-10 representatives of third party payers from Nemours service regions in Florida and the Delaware Valley will be recruited to participate in qualitative interviews about the feasibility of the TC model from that perspective. Members of the Parent, Adolescent and HCP Crowds will provide written narrative responses to open-ended questions about their perceptions of a proposed Trans-Disciplinary Care (TC) model. HCPs will participate first and their perspectives will be reflected in a revised TC model, followed by solicitation of perspectives of that model from the Adolescent and Parent Crowds. This process will be repeated as the TC Model is iteratively refined and ultimately finalized. The TC model emerging from this iterative process will be the model to be tested in the RCT.

HCPs on the Orlando and Wilmington TC teams for this study will be interviewed at the completion of TC team training and again one year later to obtain their perspectives of the training curriculum and of the structure, process and outcomes of TC care.

Adolescents with T1D and their parents who are randomized to TC will undergo qualitative interviews as they leave the study concerning their perspectives after experiencing the TC model of care delivery, its advantages and disadvantages and possible influences on efficacy.

Finally, representatives of third party payers will be interviewed after the initial RCT results have been analyzed and their perspectives will be sought regarding how these data might be interpreted from their companies' perspectives.

Quantitative (RCT) Research Component: The RCT will enroll 150 youth who have established care for T1D at either Nemours Children's Hospital in Orlando, Florida or Alfred I. du Pont Hospital for Children in Wilmington, Delaware. At least one parent or other legal caregiver of each adolescent must also participate. About 75 participants will be enrolled at each site. Oversampling of racial/ethnic minorities is expected to yield a sample comprised of at least 21 African-American and at least 21 Hispanic adolescents (At least 28% of the sample will be racial or ethnic minorities). Each parent will sign an IRB-approved Parental Permission and Informed Consent Form and thereafter each youth will sign an IRB-approved Assent Form prior to collection of any research data. Enrollment criteria for youth are: Age, At least 11, but not yet 17, years old at enrollment; T1D for at least 1 year; Most recent HbA_{1c} or mean value over the prior year 7.5% to 10.0% inclusive; Able to complete study questionnaires independently; No other chronic medical conditions that, in the opinion of the treating physician, represent obstacles to study completion. Enrollment criteria for parents are: Biological

parent or legally appointed caregiver of an enrolled patient; Primary or shared responsibility for monitoring the medical care of the youth with T1D; Able to complete study questionnaires in English; Stated intent to continue medical care for T1D at Nemours Children's Clinic for 12 months following enrollment. Two parents of the same child may participate, in which case one set of the parent-administered questionnaires will be completed at each assessment point by both parents together. Randomization will be at the level of families; for any family with two or more eligible adolescents, all of those adolescents would be randomized to the same condition. The HCPs who will implement the clinical aspects of this protocol will also be viewed as research participants and will sign IRB-approved Informed Consent Forms prior to their involvement in the research. These persons will complete questionnaires and post-study qualitative interviews about their satisfaction with the respective care models and they will also be the subject of certain questionnaires completed by parents and adolescents. Also, HCPs who see study patients will complete certain questionnaires and a qualitative interview about their perceptions of the TC model at the end of the study. Data for cost-effectiveness analyses will be collected throughout the study from parents and from participants' electronic medical records and analyzed after the RCT is complete.

Sources of research data

Qualitative research component: Transcripts of crowdsourced responses to questions posed to the Adolescent, Parent and HCP Crowds will be downloaded directly from Yammer.com and then edited to remove any identifying information. Each response will be coded for qualitative themes as described above. Qualitative interviews of representatives of key stakeholder groups will be audio-recorded and then transcribed verbatim without any personal identifiers used. Once transcribed, the audio recordings will be erased, eliminating any link between the interview respondents and their comments.

Quantitative Research Component: The data for the study will consist of blood samples for glycohemoglobin tests (HbA_{1c}), hypoglycemia diaries, glucose meter downloads, measurement of health care utilization and costs and a variety of questionnaires and interviews that pertain to family management of diabetes. The measurement schedule for the study appears in a table in the Approach section. Copies of the measures are provided in an Appendix to this application.

Potential risks

Qualitative research component: The Crowdsourcing component of the research carries the risks associated with privacy and confidentiality in that other crowd members will be able to see and read responses uploaded by any other crowd member. Participants are free to enter a response or not to any question posed to the crowd.

It is difficult to imagine any risks of participation in answering crowdsourcing questions or qualitative interviews for adolescents with diabetes, their parents, HCPs or representatives of third party payers. The only conceivable risks are threats to privacy and confidentiality. These risks are considered negligible since the interview questions will address quite innocuous content that is unlikely to be upsetting or to threaten the participants' employment, finances, health or social status in any way. Participants in the Adolescent, Parent, or HCP Crowds can simply decline to answer any question(s) that they see as threatening in any way. In our ongoing crowdsourcing study involving parents of very young children with T1D, we have not observed any clinically significant emotional or psychiatric complications associated with study participation. In fact, a number of parents have volunteered that their study participation was comforting and therapeutic.

Quantitative Research Component: As an RCT, it is possible that adolescents randomized to either the Usual Care or Trans-Disciplinary Care treatments might fare more poorly than if they had been randomized to the other treatment. Each youth's attending pediatric endocrinologist will have access to the TC team's progress notes regarding each of these patients and will retain the discretion of seeking additional consultation or other indicated services for such patients as that physician sees fit.

Adequacy of protections against risks

Qualitative research component: Transcripts of written responses will be stripped of identifiers before being forwarded to trained coders. All crowd members will be taught to respect the confidentiality of other crowd members. Members will also be aware that answering a given question is entirely optional and so they can

choose to refrain from entering a written response. Participants also have the option of sending a given response to the facilitator only rather than to the entire crowd.

Recordings of in-person interviews will be transcribed verbatim without participants' identities. Once transcribed in this way, the recordings will be erased, thus eliminating any possibility that participants could be identified if the security of the transcribed data were somehow compromised. Audio recordings will not be saved to Nemours computer network since the files on the entire network are backed up nightly, meaning that no file on the network at the time of the backup can ever be completely deleted.

Quantitative Research Component: Medical management of each enrolled patient will continue to be under the supervision of each adolescent's attending endocrinologist and the endocrinologists will have the discretion to intensify the patient's treatment, seek consultation of other professionals or pursue any other reasonable course of action deemed necessary in the patient's best interests.

Potential benefits to participants and others

Qualitative research component: Participants in our ongoing crowdsourcing study have volunteered reports indicating that sharing personal and sensitive experiences and feelings has had therapeutic effects for them by helping them to realize that their reactions are normal and shared by others in the same situation. Nonetheless, the consent documents make no claim for the prospect of direct benefits and that is how we would intend to portray the proposed work if this grant is funded.

There are no likely direct benefits to parents, adolescents or HCPs who participate in the qualitative interviews.

Quantitative Research Component: Participants randomized to any of the RCT study conditions could realize improved glycemic control, better treatment adherence, and better quality of life, although this is probably more likely for those randomized to TC-IP and TC-TH. There are unlikely to be any direct benefits to the HCPs who complete questionnaires about team function the end of the study. However, TC team members could benefit by expanding their knowledge and skill repertoires that they could apply in their T1D clinical care to patients not enrolled in this study.

Importance of the knowledge to be gained

Qualitative interview component: The knowledge to be gained in this aspect of the proposed work is essential to finalizing the optimal design of the Trans-Disciplinary Care model so that it is perceived as acceptable, feasible, safe and effective by all pertinent groups of stakeholders. Engagement of stakeholders in all phases of the research enterprise is a cornerstone of patient-centered outcomes research.

Quantitative Research Component: The RCT will determine if Trans-Disciplinary Care is more efficacious than Usual Care in terms of glycemic control, treatment adherence and various measures of psychological adjustment to diabetes among adolescents and it will analyze the incremental cost-effectiveness of implementing this model of care. The RCT will also explore whether face to face versus telehealth delivery of TC care yields differences in any of the measured outcomes. Since adolescents with T1D often struggle with management of this condition, empirical and economic validation of an alternative model of care would be extremely valuable from a public health standpoint.

Data and safety monitoring plan

Qualitative research and crowdsourcing component: There does not appear to be a need for a Data and Safety Monitoring Plan for these aspects of the proposed research since the study poses negligible risks and is not a clinical trial. There are no expected adverse events for this study. Unanticipated problems or complaints related to the research will be handled in accord with the relevant NOHSP Policy and Procedure governing such events.

Quantitative Research Component: Please see the appendix and separate document entitled "DSMP_FINAL" for a comprehensive description of the Data and Safety Monitoring Plan.

